9.4. DATA SUMMARIZATION

PD parameters and serum concentration data will be summarized by Treatment period and Cohort using the following descriptive statistics:

PD Summary Statistics:

Variable	Summarized with:
Serum concentration at each nominal time point	n, number and % BLQ, arithmetic mean, SD, CV%, minimum, median and maximum
CFB _{min} , %CFB _{min} , AUE _{CFBlast} , AUE _{%CFBlast} and TA_AUE _{CFBlast} , TA_AUE _{%CFBlast}	n, arithmetic mean, SD, CV%, minimum, median, maximum, geometric mean and geometric CV%
T _{onset} , T _{resolve} , T _{duration} , and T _{min} (actual time)	n, minimum, Q1, median, Q3 and maximum

Mean concentrations will not be presented if 50% or more of the available observations relative to total number of subjects within the treatment at any time point are missing. BLQ values for uric acid concentration will be summarized as 0 (zero) for all time points.

Samples taken outside the allowed time windows may be excluded from summarization. This will be determined prior to database lock.

The following conventions will be used for the presentation of the descriptive statistics of PD parameters and serum concentrations for uric acid:

Statistical Analysis Plan

PD Reporting Precision:

Statistics	Degree of Precision
Minimum, Maximum	3 significant digits or as needed based on actual measured values (for example PD concentrations)
Mean (arithmetic and geometric), Median	4 significant digits or as needed based on actual measured values (for example PD concentrations)
Standard deviation	5 significant digits or as needed based on actual measured values (for example PD concentrations)
CV, Geometric CV	1 decimal point or as needed based on actual measured values (for example PD concentrations)

9.5. DATA PRESENTATION FOR DUAL ENERGY COMPUTED TOMOGRAPHY (DECT) SCANS

Dual energy computed tomography (CT) scans will be performed as an exploratory measure for at least 2 subjects in Cohorts 10, 11, and 12 during the screening interval, between Days 21-28 of Treatment Period 3 (Visit 20-Visit 21), and between Days 21-30 (inclusive) of Treatment Period 5 (Visit 32) or at Early Termination to investigate changes to uric acid deposits. In addition, in any cohorts reopened for enrollment, at least 2 newly enrolled subjects per cohort will undergo DECT during the screening interval, between Days 21-28 of Treatment Period 3 (Visit 20-Visit 21), and between Days 21-30 (inclusive) of Treatment Period 5 (Visit 32) or at Early Termination to investigate changes to uric acid deposits.

Statistical Analysis Plan

In Part C, dual energy CT scans will be performed for Cohorts 13, 15, and 17 as described above.

The summary statistics at baseline, and both the changes from baseline and percent change from baseline at the specified post-baseline time points in total urate volume (mL), knee volume (mL), hand/wrist volume (mL) and foot/ankle volume (mL). In addition, line plot of individual patients for total urate volume (mL), knee volume (mL), hand/wrist volume (mL) and foot/ankle volume (mL) over post-infusion days will be provided.

9.6. DATA PRESENTATION FOR URIC ACID

The actual sampling time of uric acid blood sample collection will be listed for each cohort and will include the deviation in time from the protocol scheduled time, if applicable.

Individual subject serum concentration data and %CFB will be listed by subject, time point, and treatment group (combined placebo or dose group in relevant concentration units) and will be summarized at each time point by cohort. Baseline is defined as the last concentration of uric acid measured before dose for the 1st Treatment period and Cohort separately.

Individual subject PD parameters derived using actual measurements and %CFB will be listed for the PD analysis set in a table by subject and will be summarized, by treatment group (combined placebo or dose group) and cohort.

The table summarizing the number and % of the subjects maintaining sUA levels below 6 mg/dL at the end of treatment period 3 (week 12, visit 22) and at the end of treatment period 5 (Week 20, visit 32) will be produced.

Additionally the sUA concentrations for the week 12, visit 22 will be summarized in separate table including frequency of the subjects with sUA levels <6 mg/dL at this visit for a subset of population meeting the following eligibility criteria;

1. Patients received entire 1st doses (without drug discontinuation)
2. Patients did NOT discontinue due to a withdrawal of consent during Treatment Period 1 or TP2
3. Patients did NOT discontinue due to a protocol deviation during Treatment Period 1 or TP2
4. Patients did NOT discontinue due to NON-study drug related (OR unlikely to be study drug related) SAE during TP1 or TP2

Statistical Analysis Plan

Additionally the sUA concentrations for the week 20, visit 32 will be summarized in separate table including frequency of the subjects with sUA levels <6 mg/dL at this visit for a subset of population meeting the following eligibility criteria;

1. Patients received entire 1st doses (without drug discontinuation)
2. Patients did NOT discontinue due to a withdrawal of consent during Treatment Period 1, TP2, TP3 or TP4
3. Patients did NOT discontinue due to a protocol deviation during Treatment Period 1 or TP2
4. Patients did NOT discontinue due to NON-study drug related (OR unlikely to be study drug related) SAE during TP1 or TP2

The following figures will be produced for Uric Acid:

Mean time response profiles for uric acid concentration raw values and %CFB at each time point for each Treatment period and cohort plotted against time for each Cohort separately with curves for all Treatment periods overlaid on one plot. BLQ values for uric acid concentration will be assigned 0 values for linear scales and 1/10 of LLOQ values for all time points for the graphic representation on log-linear scales only. Actual measured concentrations will be presented on both linear and log-linear scales while %CFB profiles will be presented on linear scale only.

Box plots for each derived PD parameter based on actual measurements and %CFB: CFB_{min}, AUE_{CFBlast}, TA_AUE_{CFBlast} will also be plotted by treatment.

Individual profiles for uric acid concentration absolute values and %CFB will be plotted for each Treatment period and cohort on a separate plot.

9.7. ASSESSMENT OF THE EFFECTS OF SEL-110 (RAPAMYCIN) AND SEL-037 (PEGSITICASE) ON PD PARAMETERS OF URIC ACID

Assessments done outside the assessment windows may be excluded from summarization. This will be determined prior to database lock.

The key PD parameters based on measured values and %CFB %CFB_{min}, AUE_{%CFBlast}, and TA_AUE_{%CFBlast} as well as uric acid concentration and %CFB on day 21 of each treatment period will be analyzed using linear mixed model for the response to SEL-110 dose levels co-administered with either 0.2 or 0.4 mg/kg of SEL-037 (the dose level of SEL-110 for Cohorts 1 and 2 will be assigned as 0). Additionally contribution of SEL-110 to the PD effect of SEL-037 will be tested to compare the following (test - reference). For PD

Statistical Analysis Plan

parameters based on actual measured values baseline concentration of uric acid will be incorporated in the model as covariate.

For Parts A and B following contrasts will be tested:

Cohort 3 Part A vs Cohort 1 Part A
Cohort 5 Part A vs Cohort 1 Part A
Cohort 7 Part A vs Cohort 1 Part A
Cohort 4 Part A vs Cohort 2 Part A
Cohort 6 Part A vs Cohort 2 Part A
Cohort 8 Part A vs Cohort 2 Part A
Cohort 10 Part A vs Cohort 2 Part A
Cohort 12 Part A vs Cohort 2 Part A
Cohort 1 Part A vs Cohort 2 Part A
Cohort 3 Part A vs Part B
Cohort 5 Part A vs Part B
Cohort 7 Part A vs Part B
Cohort 4 Part A vs Part B
Cohort 6 Part A vs Part B
Cohort 8 Part A vs Part B
Cohort 10 Part A vs Part B
Cohort 12 Part A vs Part B

For Part C (cohorts 13, 15, 17) additional contrasts will be:

Cohort 13 treatment period 4 vs Cohort 11 treatment period 4
Cohort 13 treatment period 5 vs Cohort 11 treatment period 5
Cohort 15 treatment period 4 vs Cohort 11 treatment period 4
Cohort 15 treatment period 5 vs Cohort 11 treatment period 5
Cohort 15 treatment period 4 vs Cohort 13 treatment period 4
Cohort 15 treatment period 5 vs Cohort 13 treatment period 5

Cohort 17 treatment period 4 vs Cohort 11 treatment period 4
Cohort 17 treatment period 5 vs Cohort 11 treatment period 5
Cohort 17 treatment period 4 vs Cohort 13 treatment period 4
Cohort 17 treatment period 5 vs Cohort 13 treatment period 5

Cohort 17 treatment period 4 vs Cohort 15 treatment period 4
Cohort 17 treatment period 5 vs Cohort 15 treatment period 5

Statistical Analysis Plan

Unstructured variance-covariance matrix will be used. If the model cannot converge or unable to make hessian positive definite, compound symmetry or other variance-covariance matrices will be explored and used.

Example SAS code will be:

```
PROC MIXED DATA=data_set_name;  
CLASS subject_id treatment;  
MODEL loge(PD Parameter) = treatment /DDFM=KR;  
RANDOM subject_id / TYPE=UN;  
LSMEANS treatment / DIFFS CL;  
RUN;
```

1. The following hypotheses will be tested:

- $H_{01}: \mu_T/\mu_R \leq 80\%$ vs. $H_{A1}: \mu_T/\mu_R > 80\%$
and
- $H_{02}: \mu_T/\mu_R \geq 125\%$ vs. $H_{A2}: \mu_T/\mu_R < 125\%$

If the 90% confidence interval (CI) for the geometric mean ratio (GMR) is within (80% - 125%) for any of the contrasts for C_{max} , AUC_{0-t} and AUC_{0-inf} , the null hypotheses, that is H_{01} and H_{02} , will be rejected and we will conclude that the Test (T) is equivalent to the Reference (R).

2. If bioequivalence cannot be established in step 1 above, the following hypothesis will be tested to explore noninferiority (1-sided test):

- $H_{01}: \mu_T/\mu_R \leq 80\%$ vs. $H_{A1}: \mu_T/\mu_R > 80\%$

If the lower 90% CI bound for the GMR is greater than 80% for C_{max} , AUC_{0-t} and AUC_{0-inf} , H_{01} will be rejected and we will conclude that the new therapy (T=Test) is no worse than the old therapy (R=Reference).

The formula for calculation of the estimated ratio between the test and reference and the $(1-2*\alpha)*100\%$ CI of the ratio is given below.

Difference = Estimate of difference between test and reference least square means

Statistical Analysis Plan

$$Ratio = 100 \times e^{Difference}$$

(1-2* α)*100% CIs for the Ratio:

$$Lower = 100 \times e^{(LowerBound (1-2*\alpha)\%CIs for theDifference)}$$

$$Upper = 100 \times e^{(UpperBound (1-2*\alpha)\%CIs for theDifference)}$$

GMR ratio outside equivalence criteria 80-125% will demonstrate (1) dose effect SEL-110; (2) synergy or additive effect of SEL-110 administration on PD by SEL-037. P-values will be generated for all contrasts. Values of $p < 0.05$ will indicate statistical significance of the effect.

The results of the comparisons will be graphically illustrated using box plots for Part A/B and comparison between Part C and B separately.

Correlations between PD endpoints (C_{min} , CFB_{min} , $AUE_{CFBlast}$, and $TA_AUE_{CFBlast}$) and PK parameters (C_{max} , AUC_{0-last} and AUC_{0-inf}) for both SEL-110 and SEL-037 will be explored using Spearman correlation analysis. The correlations for Part C treatment periods will be presented in the separate table.

The correlation between each of these PK (C_{max} , AUC_{0-last} and AUC_{0-inf}) and PD (C_{min} , CFB_{min} , $AUE_{CFBlast}$, and $TA_AUE_{CFBlast}$) parameters will also be explored and presented in a scatter plot with a regression line on it using simple linear regression which will have PK parameter as dependent variable and PD parameter as independent variable. The additional plots will be created for the Part C.

Example SAS code will be:

```
PROC GLM DATA=PKPDDATA;  
MODEL PD_parameter = PK_parameter;  
RUN;
```

Statistical Analysis Plan

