6.3.1. Stopping Rules in an Individual Subject or in a Cohort

For this clinical trial a treatment period is defined as period of time from the beginning of dosing of the first study drug on a given dosing day (ie, Either saline placebo or SEL-110 during Part A of the study and SEL-037 during Part B of the study) to the beginning of the next scheduled dose of study drug, and has a typical duration of 28 days.

For Part C (Cohorts 13, 15, and 17), a treatment period is defined as the period of time from the beginning of dosing of SEL-212 to the beginning of the next scheduled dose of study drug.

Individual

For subjects in Cohorts 1 and 2, any subject who has a weekly serum uric acid value ≥ 6 mg/dl or $>50\%$ of their baseline (where baseline value refers to the pre-dose serum uric acid level from visit 4, Day 0, treatment period 1) at Day 21 of their current treatment cycle will not be eligible for the next dosing of SEL-037. The subject will be followed for 30 days post the last dose of study drug at which time they will have an End of Study assessment and their participation in the study will be terminated.

In Cohorts 3-8, 10-13, 15, and 17 only subjects whose ambient blood samples indicate a serum uric acid (sUA) value less than or equal to 1.0 mg/dL at any of the Day 21 visits will be eligible for the next dosing of SEL-212 (or SEL-037). All other subjects will be followed for 30 ± 2 days post the last dose of study drug at which time all of the End of Study assessments will be completed and their participation in the study will be terminated.

Cohort

If 5 subjects in any of Cohorts 1-5 or 7, or if 10 subjects in any of Cohorts 6, 8, 10, 11, or 12 have met the requirements for individual stopping of their participation in the trial as described above or have been stopped based on Section 6.4 then that cohort will no longer have any additional subjects enrolled in it. Those subjects who have been enrolled will continue until they fulfill the requirements

Study: SEL-212/201 Version: 7.1	Effective Date March 19, 2018
------------------------------------	----------------------------------

for individual stopping or complete the clinical trial treatment periods. If they continue to meet the requirements for continued participation they may continue in Part B of the study.

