9.3. PHARMACODYNAMICS PARAMETERS

The following PD parameters will be calculated based on actual measurements of PD uric acid for each Cohort and Treatment period and Overall where possible:

C_{min}	Minimal observed serum concentration
T_{min}	Time of minimal observed serum concentration
CFB_{min}	Minimum observed change from baseline in serum concentration
$AUE_{CFBlast}$	Absolute value for Area under the change from baseline in effect-time curve from time zero to the time of the last quantifiable concentration (effect - uric concentration)
$TA_{AUE_{CFBlast}}$	Time adjusted area under the absolute value for effect-time curve from time zero to the time of last quantifiable concentration (effect - uric concentration)
T_{onset}	Time of onset of effect - first time point of reduction uric acid concentration >10% of baseline
$T_{resolve}$	Time of resolution of effect - first time point of return of uric acid concentration to baseline defined as <10% difference from pre-dose baseline
$T_{duration}$	Time of duration of effect, calculated as $T_{resolve} - T_{onset}$

The following PD parameters will be calculated based on %CFB of PD uric acid for each Cohort and Treatment period and Overall where possible

Statistical Analysis Plan

$\%CFB_{\min}$	Minimum %CFB in serum concentration
$AUE_{\%CFB_{\text{last}}}$	Absolute value for Area under the %CFB in effect-time curve from time zero to the time of the last quantifiable concentration (effect - uric concentration)
$TA_AUE_{\%CFB_{\text{last}}}$	Time adjusted area under the %CFB for effect-time curve from time zero to the time of last quantifiable concentration (effect - uric concentration)
# and % of patients with $SUA < 6$ in TP3	The number and % of patients maintaining sUA concentrations below 6 mg/dL at the end of treatment period 3
# and % of patients with $SUA < 6$ in TP5	The number and % of patients maintaining sUA concentrations below 6 mg/dL at the end of treatment period 5

9.3.1. Handling of Dropouts, Missing Data or Data Below the Lower Limit of Quantification

Missing concentration data for all subjects who are administered scheduled study treatments will be considered as non-informative missing and will not be imputed. No concentration estimates will be provided for missing sample values.

For the derivation of PD parameters, serum concentration summary, individual serum concentration versus time curves and mean concentration versus time graphs the following rules will apply:

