15.2.5.2. Table Conventions

- Units will be included where available
- If the categories of a parameter are ordered, then all categories between the maximum and minimum category should be presented in the table, even if n=0 for all treatment groups in a given category that is between the minimum and maximum level for that parameter. For example, the frequency distribution for symptom severity would appear as:

Severity Rating	N
severe	0

Statistical Analysis Plan

moderate	8
mild	3

Where percentages are presented in these tables, zero percentages will not be presented and so any counts of 0 will be presented as 0 and not as 0 (0%).

- If the categories are not ordered (e.g., Medical History, Reasons for Discontinuation from the Study, etc.), then only those categories for which there is at least 1 subject represented in 1 or more groups should be included.
- An Unknown or Missing category should be added to any parameter for which information is not available for 1 or more subjects.
- Unless otherwise specified, the estimated mean and median for a set of values should be printed out to 1 more significant digit than the original values, and standard deviations should be printed out to 2 more significant digits than the original values. The minimum and maximum should report the same significant digits as the original values. For example, for systolic blood pressure:

N	XX
Mean (SD)	XX.X (XX.XX)
Median (Min, Max)	XX.X(XX.X, XX.X)
95% CI	(XX,XX, XX,XX)

- P-values should be output in the format: “0.xxx”, where xxx is the value rounded to 3 decimal places. Any p-value less than 0.001 will be presented as <0.001. If the p-value should be less than 0.0001 then present as <0.0001. If the p-value is returned as >0.999 then present as >0.999
- Percentage values should be printed to one decimal place, in parentheses with no spaces, one space after the count (e.g., 7 (12.8%), 13 (5.4%)). Pre-determine how to display values that round down to 0.0. A common convention is to display as '<0.1', or as appropriate with additional decimal places. Unless otherwise noted, for all percentages, the number of subjects in the analysis set for the treatment group who have an observation will be the denominator. Percentages after zero counts should not be displayed and percentages equating to 100% should be presented as 100%, without any decimal places.

Statistical Analysis Plan

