- Tabular display of data for medical history, prior / concomitant medications, and all tabular displays of adverse event data should be presented by the body system, treatment class, or SOC with the highest occurrence in the active treatment group in decreasing order, assuming all terms are coded. Within the body system, drug class and SOC, medical history (by preferred term), drugs (by ATC1 code), and adverse events (by preferred term) should be displayed in decreasing order. If incidence for more than 1 term is identical, they should then be sorted alphabetically. Missing descriptive statistics or p-values which cannot be estimated should be reported as “-”.
- The percentage of subjects is normally calculated as a proportion of the number of subjects assessed in the relevant treatment group (or overall) for the analysis set presented. However, careful consideration is required in many instances due to the complicated nature of selecting the denominator, usually the appropriate number of subjects exposed. Describe details of this in footnotes or programming notes.
- For categorical summaries (number and percentage of subjects) where a subject can be included in more than one category, describe in a footnote or programming note if the subject should be included in the summary statistics for all relevant categories or just 1 category and the criteria for selecting the criteria.
- Where a category with a subheading (such as system organ class) has to be split over more than one page, output the subheading followed by “(cont)” at the top of each subsequent page. The overall summary statistics for the subheading should only be output on the first relevant page.

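### The percentage with sUA below 6 mg/dL at visits 22 and 32 defaults to subjects with a value, who must already have passed three or four Day-21 sUA gates

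*SAP*

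**What the plan says.** SAP 9.3 lists as a PD parameter "The number and % of patients maintaining sUA concentrations below 6 mg/dL at the end of treatment period 3", with a matching entry for period 5. SAP 9.6 turns these into one table of the number and percentage of "subjects maintaining sUA levels below 6 mg/dL at the end of treatment period 3 (week 12, visit 22"), and likewise at visit 32. It adds two tables restricted to subsets defined by eligibility criteria. Neither section says who is in the denominator or how a subject stopped before the visit is counted, and no analysis set is named for the main table.

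The general rules are in SAP 15.2.5.2. Unless otherwise noted, "the number of subjects in the analysis set for the treatment group who have an observation will be the denominator". A later bullet begins in agreement: "The percentage of subjects is normally calculated as a proportion of the number of subjects assessed in the relevant treatment group". It then warns that "careful consideration is required in many instances due to the complicated nature of selecting the denominator, usually the appropriate number of subjects exposed", and leaves the details to footnotes or programming notes.

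Protocol 6.3.1 decides who is dosed again. In the SEL-212 cohorts it is "only subjects whose ambient blood samples indicate a serum uric acid (sUA) value less than or equal to 1.0 mg/dL" at Day 21. In Cohorts 1 and 2 a subject is stopped if Day-21 sUA is 6 mg/dL or more, or above half of baseline. Stopped subjects have End of Study assessments about 30 days after their last dose and then leave. SAP 6.1 lists Early Termination data without summarizing them. SAP 9.3.1 treats missing sUA as non-informative and does not impute it.

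**The concern.** Whether a subject has a value at visit 22 or 32 depends on that subject's earlier sUA, which is the outcome being summarized. Under the default denominator, subjects who lost response leave both numerator and denominator, and the percentage moves towards 100% however many were stopped. SAP 9.4 withholds mean concentrations when half or more of the observations are missing, but no such guard is written for these percentages.

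A rate of subjects maintaining sUA below 6 mg/dL will naturally be read as a share of those treated. The gates also differ between Cohorts 1-2 and the SEL-212 cohorts, so percentages shown by cohort would be conditioned on different things.

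**Working it through.** The plan states no rate, expected count or power for this endpoint, so there is no figure to reproduce.

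**1. Gates before each visit.** Periods last 28 days, and the gate in period k falls on study day 28(k-1) + 21, giving Days 21, 49, 77 and 105 for periods 1 to 4. Visit 22 is period 4 Day 0 (schedule of events, Part B): 3 x 28 = Day 84. Three gates precede it, the last by 84 - 77 = 7 days. Visit 32 is period 5 Day 21: 4 x 28 + 21 = Day 133, after four gates. This takes the Day-21 value of each period as governing the next dose.

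**2. Stopped subjects.** A SEL-212 subject stopped at the third gate was last dosed on Day 56 and is assessed at 56 + 30 (±2) = Days 84-88. One stopped at the fourth gate is assessed at 84 + 30 (±2) = Days 112-116. These values exist, but SAP 6.1 appears to treat them as Early Termination data, which do not enter the visit tables.

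**3. Subset criteria.** One Week-12 criterion reads "Patients did NOT discontinue due to a protocol deviation during Treatment Period 1 or TP2". The other two discontinuation criteria cover withdrawn consent and unrelated SAEs in the same periods. Anyone who left in period 1 or 2 has no visit 22 value, so under observed-only counting these three criteria remove nobody. They have an effect only if subjects without a value stay in the denominator, which suggests observed-only counting was not intended there. Subjects stopped by the sUA rule are not excluded from either subset, and the SAP does not say how to count them.

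**4. Illustration (stop counts assumed).** Take 20 dosed subjects, the upper cohort size, with 10 stopped before visit 22 and all the others below 6 mg/dL.
- Observed only: 10/10 = 100% (exact 95% CI 69.2-100).
- All subjects, stops counted as not maintaining: 10/20 = 50% (27.2-72.8).
- All subjects, stops classified by last value, if 3 or 5 of the 10 were below 6: 13/20 = 65% or 15/20 = 75%.

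With 4 or 7 of 20 stopped, the ceiling when stops count as not maintaining is 16/20 = 80% or 13/20 = 65%.

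**5. Range over assumed gate pass rates.** If stops count as not maintaining, the observed-only rate is too high by 1/(share reaching the visit). For a constant pass rate q, the share is q³ at visit 22 and q⁴ at visit 32.

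| Assumed q | Share at visit 22 / 32 | Factor at visit 22 / 32 |
|---|---|---|
| 0.95 | 0.857 / 0.815 | 1.17 / 1.23 |
| 0.90 | 0.729 / 0.656 | 1.37 / 1.52 |
| 0.70 | 0.343 / 0.240 | 2.92 / 4.16 |

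No pass rate is given in the documents. The table shows sensitivity and is not evidence about this trial.

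**6. Different gates.** For an assumed baseline of 8 mg/dL, half of baseline is 4.0. Subjects stopped while still below 6 mg/dL are those above 1.0 in SEL-212 cohorts, but only those above 4.0 in Cohorts 1-2.

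**The case against.** The strongest reply is that the SAP already shows the attrition. SAP 15.2.4 puts the analysis-set size in each column heading, and SAP 15.2.5.2 requires an Unknown or Missing category wherever information is lacking for any subject. In the illustration the table should carry N=20, 10 below 6 mg/dL and 10 Missing, so a reader can form 10/20. SAP 7.1 tabulates reasons for early termination, and SAP 10.4 includes a Day-21 table split at 1.0 mg/dL. This stands: one might infer that the tables would hide the losses, and the documents do not support that. What remains is that the printed percentage is the conditional one and the Missing row does not separate sUA-rule stops from other losses.

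A reader might also infer that the table conventions flatly contradict each other. They do not. The first is a definite default, the second opens by agreeing with it, and the remark about subjects exposed is a general caution that does not clearly override it. The Week-12 criteria could simply be redundant.

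Nor can it be claimed that every subject observed at visit 22 in a SEL-212 cohort was at or below 1.0 mg/dL a week earlier. The protocol's reference to any of the Day-21 visits is loose. The revision history also records changes to the individual stopping rules in versions 03 and 05.1, after the estimated first enrolment in October 2016, so some early subjects may have been dosed under other rules.

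Finally, the cohort closure count of 10 covers stops at any gate. It does not show that 10 subjects would be lost before visit 22.

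**Conclusion.** The point holds in limited form. With no denominator in SAP 9.3 or 9.6, the default applies, and the resulting percentage is conditional on having kept qualifying for dosing. It is biased upward as a statement about treated subjects, provided stopped subjects are less often below 6 mg/dL at the visit than those who continue. The gate count of three and four rests on the current protocol rule and on reading each period's Day-21 value as decisive.

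The size is unknown. The 100% against 50% contrast is an illustration with an assumed number of stops.

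These are descriptive secondary PD outputs in a study whose primary objective is safety. No between-cohort test of these rates is planned, and the all-subject proportion should be recoverable from the table. Severity is minor to should-fix.

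**What to change.** In SAP 9.6:

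1. Override the 15.2.5.2 default. Use all PD-set subjects in the cohort as the denominator, or all members of the defined subset in the subset tables.
2. Show subjects stopped by the Day-21 sUA rule and subjects missing for other reasons as separate rows within that denominator, alongside n dosed, n with a visit value and n below 6 mg/dL.
3. Report the rate with sUA-rule stops counted as not maintaining. Beside it, give a version that classifies those subjects by last available sUA (Day 21, or the assessment about 30 days after the last dose). The second version is needed because the first counts some subjects stopped while below 6 mg/dL as not maintaining.
4. Label any observed-only rate as applying to subjects who continued dosing, and note that the gates differ between Cohorts 1-2 and the SEL-212 cohorts.

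Two small items belong in the same edit. The SAP labels visit 32 as Week 20, but Day 133 is Week 19 (133/7). In the Week-20 subset, one criterion reads "Patients did NOT discontinue due to a withdrawal of consent during Treatment Period 1, TP2, TP3 or TP4", while the protocol-deviation and SAE criteria stop at period 2; the periods should be aligned.

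The cost is a few sentences, reprogramming of the existing tables and one more table. No new data are needed and no dosing or stopping rule changes. The drawback is that the reported rates will look less favourable.
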